	
 b. squamous cell skin cancer c. in situ cervical cancer d. in situ bladder cancer 
8) Prior treatment with cabiralizumab 9) Prior treatment with nivolumab or other medications within the checkpoint blockade family.
 
Please see body of protocol for full exclusion criteria.

STATISTICAL CONSIDERATIONS	
We propose a two-stage design with co-primary endpoints of complete response (CR) and overall response (OR), testing a “both-and” null hypothesis against an “either-or” alternative hypothesis. Specifically, we posit that a CRR of 30% or ORR of 60% is achievable. Initially, 17 eligible patients will be followed for response. At this point, if fewer than 3 patients demonstrate CR (<18%) and fewer than 7 patients demonstrate OR (<41%), the trial will be stopped for futility. Otherwise, we will enroll an additional 16 patients, and the trial will successfully conclude if at least 7 patients (out of 33 total) demonstrate CR (21%) or at least 17 patients demonstrate OR (52%). When the true CRR and ORR are simultaneously no greater than 10% and 30%, respectively, this design will successfully conclude with probability at most 0.05 (one-sided type I error) and stop at the interim analysis with probability at least 0.75. When the true CRR is at least 30% or the true ORR is at least 60%, this design will successfully conclude with probability at least 0.62 (power) and stop for futility at the interim analysis with probability at most 0.34.
 
Multiple Grade 4+ adverse event (AE) stopping rules will be applied during enrollment of the first 17 patients. First, enrollment will stop for any grade 4 AE observed in ≥ 7 (7/17=41%) patients. Second, enrollment will stop for grade 4 AE requiring discontinuation of treatment, as specified in the protocol, observed in ≥ 3 (3/17=12%) of patients. Third, enrollment will stop if any Grade 5 AE is observed within the first 17 subjects.
 
Peripheral T-cell lymphoma response and progression will be assessed using the provisional Lugano lymphoma response to immunomodulatory therapy criteria (LYRIC). Additional secondary endpoints include response by Lugano criteria, PFS, DCR, DOR, and TNT. Safety assessments will consist of the surveillance and recording of AEs and documentation of physical examination findings and laboratory data. Type, incidence, severity, seriousness, and relatedness of adverse events will be recorded.

TOTAL NUMBER OF SUBJECTS	33

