11. ADVERSE EVENTS

11.1 Definitions

11.1.1 Adverse Event (AE)

An AE is any untoward medical occurrence whether or not considered related to the study drug that appears to change in intensity during the course of the study. The following are examples of AEs:

- Unintended or unfavorable sign or symptom
- A disease temporally associated with participation in the protocol
- An intercurrent illness or injury that impairs the well-being of the subject

Abnormal laboratory values or diagnostic test results constitute AEs only if they induce clinical signs or symptoms or require treatment or further diagnostic tests

Hospitalization for elective surgery or routine clinical procedures that are not the result of an AE (e.g., surgical insertion of central line) should not be recorded as an AE.

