11.2 Reporting

11.2.1 Adverse Events

- AEs will be recorded from time of signed informed consent until 100 days after discontinuation of study drug(s).
- AEs will be recorded regardless of whether or not they are considered related to the study drug(s).
- All AEs will be recorded in the subject's medical record and on the appropriate study specific eCRF form within the EDC system.
- All AEs considered related to study drug(s) will be followed until resolution to \leq Grade 1 or baseline, deemed clinically insignificant, and/or until a new anti-cancer treatment starts, whichever occurs first.
- Asymptomatic laboratory abnormalities that do not require treatment will not be collected as adverse events.

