12.3 Sample Size, Accrual, and Interim Futility Analysis

We propose a two-stage design with co-primary endpoints of complete response (CR) and overall response (OR), testing a “both-and” null hypothesis against an “either-or” alternative hypothesis. Specifically, we posit that a CRR of 30% or ORR of 60% is achievable (note that CRR refers to the *marginal* CRR, that is, the complete response rate without respect to overall response status, and not the *conditional* CRR, which would be the complete response rate among any responders). Initially, 17 eligible patients will be followed for response. At this point, if fewer than 3 patients demonstrate CR (<18%) and fewer than 7 patients demonstrate OR (<41%), the trial will be stopped for futility.

Otherwise, we will enroll an additional 16 patients, and the trial will successfully conclude if at least 7 patients (out of 33 total) demonstrate CR (21%) or at least 17 patients demonstrate OR (52%).

We will also formally incorporate three Grade 4+ adverse event (AE) thresholds that will activate at the interim analysis. First, if the number of patients with any Grade 4 AE is greater than or equal to 7 (7/17=41%) by the interim analysis, enrollment will stop. Second, if the number of patients with Grade 4 AEs that *require discontinuation of study treatment, as specified in section 6.3*, is greater than or equal to 3 (3/17=12%) by the interim analysis, enrollment will stop. Third, enrollment will stop at the interim analysis for any Grade 5 AE attributable to drug.

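### The synopsis and Section 12.3 give different Grade 5 stopping rules: a fatal AE judged unrelated to study drug stops enrolment under one and not under the other

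*Combined protocol and SAP*

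**What the plan says.** The synopsis (Statistical Considerations) and Section 12.3 each list three safety rules for the first 17 patients. The first two match in substance: 7 or more patients with any Grade 4 AE, and 3 or more with a Grade 4 AE requiring discontinuation.

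The third differs:

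- Synopsis: "Third, enrollment will stop if any Grade 5 AE is observed within the first 17 subjects".
- Section 12.3: "Third, enrollment will stop at the interim analysis for any Grade 5 AE attributable to drug".

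The stated timing differs too:

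- Synopsis: "Multiple Grade 4+ adverse event (AE) stopping rules will be applied during enrollment of the first 17 patients".
- Section 12.3: "We will also formally incorporate three Grade 4+ adverse event (AE) thresholds that will activate at the interim analysis".

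Section 11.1.1 makes the AE definition independent of causality: "An AE is any untoward medical occurrence whether or not considered related to the study drug". Section 11.2.1 has unrelated AEs recorded as well. Section 11.1.4 grades relatedness on five levels (unrelated, unlikely, possible, probable, definite). Section 11.1.2 keeps deaths from disease progression out of SAE reporting unless the site investigator attributes them to study drug.

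For the second rule, Section 12.3 stops when the count "is greater than or equal to 3 (3/17=12%) by the interim analysis, enrollment will stop". The synopsis prints the same fraction and percentage.

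**The concern.** The Grade 5 rule acts on a single event, so its wording decides the outcome. Because AEs include unrelated events, the synopsis rule is strictly wider than the Section 12.3 rule. After one fatal AE judged unrelated, a reader of the synopsis halts enrolment and a reader of Section 12.3 continues. No other safety rule settles the matter, since the Grade 4 rules need 7 or 3 patients.

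Two gaps widen the uncertainty. Section 12.3 does not say which of the five relatedness levels count as attributable, so a fatal AE rated possible is unresolved even under that text. Neither version says whether a progression death counts as a Grade 5 AE for stopping; Section 11.1.2 speaks only to SAE reporting.

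At stake is a decision to halt or continue a 33-patient trial after a death, with the site, the sponsor-investigator and the DSMC able to cite different texts. The printed operating characteristics are also affected if the wider rule is the intended one.

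**Working it through.** **1. The two rules side by side (first 17 patients)**

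| Event | Synopsis | Section 12.3 |
|---|---|---|
| Fatal AE, related to drug | stop | stop |
| Fatal AE, unrelated, not progression | stop | continue |
| Progression death, not attributed to drug | not stated | continue |
| Fatal AE rated possible | stop | not defined |

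The conflict is textual and rests on no calculation.

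**2. The percentage.** 3/17 = 0.1765, or 18%; 2/17 = 0.1176, or 12%. The count of 3 is explicit in both places.

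**3. The plan's own operating characteristics (Section 12.3).** Inputs: 17 + 16 patients; futility stop if CR < 3 and OR < 7; success if CR ≥ 7 or OR ≥ 17 of 33; null CRR 10% and ORR 30%; Grade 4+ AE rate 32%. I enumerated the trinomial outcome (CR, PR, no response) exactly, took AEs as independent of response, and applied only the ≥7/17 safety rule.

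- Efficacy rules alone: CRR 30%/ORR 30% gives success 0.8674 and stop 0.0774; the null gives stop 0.6492.
- P(Bin(17, 0.32) ≤ 6) = 0.7162.
- Minimum power = 0.8674 × 0.7162 = 0.621 (stated: at least 0.62).
- Maximum stop under the alternative = 1 − (1 − 0.0774) × 0.7162 = 0.339 (stated: at most 0.34).
- Stop under the null = 1 − (1 − 0.6492) × 0.7162 = 0.749 (stated: about 0.75).

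The stated figures are reproduced without rules 2 and 3.

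**4. How often the texts would disagree.** Let r be the per-patient rate of unrelated Grade 5 AEs by the interim and d the drug-related rate. Both are assumptions. The texts disagree when at least one unrelated and no drug-related Grade 5 AE occurs among 17:

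P = (1 − d)^17 − (1 − d − r)^17

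| r | d = 0 | d = 1% |
|---|---|---|
| 0.5% | 0.082 | 0.070 |
| 1% | 0.157 | 0.134 |
| 2% | 0.291 | 0.247 |
| 5% | 0.582 | 0.494 |

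Section 1.6.2.1 reports no Grade 5 AE among 24 monotherapy subjects and none of 14 deaths due to an AE, which favours the low end. The one-sided 95% upper bound for 0/24 is 1 − 0.05^(1/24) = 0.117, so those data do not exclude any rate in the table.

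**5. Effect of choosing the all-cause rule.** Take d = 0 and unrelated Grade 5 AEs independent of response and of Grade 4 AEs. Power becomes 0.621 × (1 − r)^17, and the maximum stop becomes 1 − (1 − 0.339) × (1 − r)^17.

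| r | (1 − r)^17 | Power | Maximum stop |
|---|---|---|---|
| 0.5% | 0.918 | 0.57 | 0.39 |
| 1% | 0.843 | 0.52 | 0.44 |
| 2% | 0.709 | 0.44 | 0.53 |
| 5% | 0.418 | 0.26 | 0.72 |

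**The case against.** The best case against is that the documents already lean towards Section 12.3. That section says it formally incorporates the thresholds, Sections 12.6.1 and 12.6.2 refer back to it, and the synopsis defers to the body for the full exclusion criteria and, in rule 2, for discontinuation: "Second, enrollment will stop for grade 4 AE requiring discontinuation of treatment, as specified in the protocol". Both texts stop for a drug-related death, which is the safety-critical case. SAEs are reported within 1 business day (Section 11.2.2.1), the sponsor-investigator promptly assesses relatedness (11.2.2.3), and the DSMC can raise immediate concerns (13.2). Progression, a likely main cause of death in this population, is largely outside the conflict because of Section 11.1.2.

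Most of this stands. It shows which version should be the default and narrows the conflict to fatal AEs that are neither drug-related nor due to progression. It does not remove the conflict: the synopsis does not defer to the body on the Grade 5 rule, and prompt reporting does not tell the DSMC which rule it is applying.

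The timing difference is minor. The Section 12.3 thresholds are cumulative counts, so checking continuously or at patient 17 changes when enrolment stops, not whether stage 2 opens.

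Three stronger readings are tempting and not supported:

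- *That the simulations left out rules 2 and 3.* The ≥7/17 rule alone matches the printed figures, but so does adding a 2% discontinuation-AE rate with no Grade 5 AEs (0.620, 0.341, 0.749). An assumed 0.1% Grade 5 rate gives 0.6125 and 0.3485, which round to 0.61 and 0.35. Yet these lie only 0.0025 and 0.0035 from the rounding limits 0.615 and 0.345. The printed values are simulated with no replicate count; even at 10,000 replicates the standard error would be √(0.6125 × 0.3875 / 10,000) ≈ 0.005. What was assumed for these rules is a reporting query only.
- *That the 12% shows a threshold of 2 was meant.* The count of 3 is explicit in both places.
- *That continuing under Section 12.3 exposes patients to drug harm.* The texts part only on deaths judged unrelated to drug.

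**Conclusion.** The inconsistency is real and wrong as written. One fatal AE judged unrelated among the first 17 patients stops enrolment under the synopsis and not under Section 12.3, and no clause sets precedence. The scope is narrow, for the reasons above.

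The conflict and the 3/17 error rest on the text alone. The disagreement probabilities of 0.08 to 0.58 (d = 0) rest wholly on assumed rates and are illustrative. The visible text gives no rate of unrelated Grade 5 AEs, and part of the safety summary in Section 1.6.2 was not available for this review, so a relevant rate may be stated there. The power losses in step 5 also assume independence and apply only if the all-cause rule is chosen.

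**What to change.** Put one rule set, word for word, in the synopsis and Section 12.3. By default use the drug-attributable version, for example:

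> Enrolment stops if, among the first 17 treated patients, any of these is met: one Grade 5 AE possibly, probably or definitely related to study drug (Section 11.1.4), not counting deaths from progression that are not attributed to study drug; 3 patients (3/17 = 18%) with a Grade 4 AE requiring discontinuation under Section 6.3; 7 patients (7/17 = 41%) with any Grade 4 AE.

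Then state one timing in both places. If the rules are checked continuously, as the synopsis says, name who keeps the running count; this is a small added monitoring task for Section 12.3, and existing SAE reporting would feed it. If they are checked at the interim, change the synopsis.

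Add one sentence giving the discontinuation-AE and Grade 5 rates used in the simulations, or saying that the printed figures cover futility and rule 1 only.

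The cost is a wording amendment in two places, with no change in sample size and, under the default rule, no re-simulation required by the harmonisation itself. If the sponsor chooses the all-cause rule instead, the 0.62 power and 0.34 stopping probability must be recomputed with a stated all-cause Grade 5 rate.

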12.4 Assessment of Safety

Any subject who receives at least one dose of treatment on protocol will be evaluated for safety using CTCAE v5.

12.5 Assessment of Efficacy

All subjects with measurable disease who have received at least one cycle of treatment and have their disease re-evaluated will be evaluable for assessment of objective response.

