9.3.2 Objective Response Rate

The objective response rate is the proportion of all subjects with confirmed PR or CR.

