9.3.3 Complete Response Rate

The complete response rate is the proportion of all subjects with confirmed CR.

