12.2 Endpoints

12.2.1 Definition of Primary Endpoints

See Section 9.3.

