12.6 Data Analysis Plans

The primary analysis will compare the observed OR and CR rates to posited null values of 30% and 10%, respectively. We will calculate score-based confidence intervals for binomial proportions. At the critical values of 17/33 and 7/33, the confidence intervals for the ORR and CRR would be (35.2%, 67.5%) and (10.7%, 37.8%), respectively. The analyses of secondary safety objectives will be conducted using tabulations of adverse events, stratified by grade and attribution.

The analyses corresponding to secondary efficacy endpoints (PFS, DCR, DOR, TNT) will be summarized with typical ‘time-to-event’ analyses.

With regard to the exploratory objectives, we will evaluate pre-post changes in LAM, Treg, CTL, “exhausted” T cell, and MDSC densities, as well as lymphoma cell and tumor microenvironment expression of PD-L1 and CSF-1R. We posit that changes in some or all of these biomarkers will correlate with response, thus demonstrating potential as prognostic biomarkers. We will also evaluate MRD status in patients achieving CR and hypothesize that patients with CR but detectable MRD will predict relaps. We will quantify these associations using visual and statistical summarization.

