12.6.1 Analysis Plans for Primary Objective

See section 12.3.

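### Section 12.5 makes only re-evaluated subjects evaluable for response, while 9.3.2, 9.3.3, 12.3 and 12.6 count all subjects; used as the denominator, 12.5 would raise the reported ORR, CRR and score intervals

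*Combined protocol and SAP*

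**What the plan says.** The endpoint definitions use one denominator. Section 9.3.2: "The objective response rate is the proportion of all subjects with confirmed PR or CR". Section 9.3.3: "The complete response rate is the proportion of all subjects with confirmed CR". Section 12.2.1 refers to Section 9.3 for the primary endpoints.

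The design uses fixed totals. Section 12.6.1 refers the primary analysis to 12.3, which begins: "Initially, 17 eligible patients will be followed for response". The trial stops for futility with fewer than 3 CR and fewer than 7 OR among those 17. It succeeds with at least 7 CR or at least 17 OR among 33. Section 12.6 compares the observed rates with nulls of 30% (OR) and 10% (CR) and gives score intervals on 33: "At the critical values of 17/33 and 7/33, the confidence intervals for the ORR and CRR would be" 35.2% to 67.5% and 10.7% to 37.8%.

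Section 12.5 differs. Given measurable disease, those who "have received at least one cycle of treatment and have their disease re-evaluated will be evaluable for assessment of objective response". It does not say whether being evaluable sets the denominator. No section says how a subject without a re-evaluation is counted, or whether such a subject is replaced.

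**The concern.** Section 12.5 follows directly on 12.4, which sets the safety population, so an analyst could naturally take it as the efficacy population. On that reading, a subject who dies or leaves before any response assessment drops out of the denominator. Such a subject cannot have a confirmed response, so the exclusion depends on outcome and works in one direction only.

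The primary objectives are to estimate ORR and CRR, so the reported rates and intervals are the trial's main product. If the denominator is left open, it could be settled after the results are known.

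**Working it through.** **1. Reproduce the plan's intervals.** Wilson score limits, with p = x/n and z = 1.96: [p + z²/2n ± z√(p(1−p)/n + z²/4n²)] / (1 + z²/n). Section 12.6 does not state the level; 95% two-sided without continuity correction matches.
- 17/33 = 51.5%: 35.2% to 67.5%, as printed.
- 7/33 = 21.2%: 10.7% to 37.8%, as printed.

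**2. Reproduce the operating characteristics on full denominators.** Exact trinomial enumeration (CR nested in OR, 17 + 16 subjects, rules of 12.3), with the 7-of-17 Grade 4 rule at a 32% AE rate taken as independent of response. P(Bin(17, 0.32) ≤ 6) = 0.716.
- Null (CRR 10%, ORR 30%): success 0.0418 × 0.716 = 0.030 (stated: below 0.05). Interim stop 1 − 0.716 × (1 − 0.649) = 0.749 (stated: about 0.75).
- CRR 30%, ORR 30%: success 0.867 × 0.716 = 0.621 (stated: at least 0.62).

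The stated properties therefore correspond to full denominators of 17 and 33.

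**3. Effect on the reported rate.** With x responders and k subjects outside 12.5, the rate is x/(33 − k) instead of x/33, a factor of 33/(33 − k). The documents do not give k; 1 to 5 is an assumed range. The OR and CR columns give the smallest count whose 95% lower limit exceeds the null.

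| k | factor | true 30% / 10% appears as | OR count, limit > 30% | CR count, limit > 10% |
|---|---|---|---|---|
| 0 | 1.00 | 30.0% / 10.0% | 16 | 7 |
| 1 | 1.03 | 30.9% / 10.3% | 15 | 7 |
| 2 | 1.06 | 31.9% / 10.6% | 15 | 7 |
| 3 | 1.10 | 33.0% / 11.0% | 14 | 7 |
| 5 | 1.18 | 35.4% / 11.8% | 14 | 6 |

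Examples, with lower limits in parentheses:
- OR: 15/33 = 45.5% (29.8%) becomes 15/32 = 46.9% (30.9%).
- OR: 14/33 = 42.4% (27.2%) becomes 14/30 = 46.7% (30.2%).
- CR: 6/33 = 18.2% (8.6%) becomes 6/28 = 21.4% (10.2%).

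**4. Effect on the decision.** The rule counts responders. With 33 subjects and no replacement, dropping non-responders from a denominator leaves the counts as they were. Counts of 14 or 15 OR stay short of 17, and 6 CR stays short of 7. Type I error stays at 0.030 (0.042 without the toxicity rule).

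**5. Replacement, a separate question.** Let m be the unassessed share. All figures include the toxicity rule at 32%.
- With replacement, and nulls assumed to apply to all enrolled, the enumeration runs at 0.10/(1 − m) and 0.30/(1 − m). Type I error is 0.0555 × 0.716 = 0.040 at m = 5% and 0.0748 × 0.716 = 0.054 at m = 10%.
- Without replacement, and alternatives assumed to describe assessed patients, it runs at the alternatives times (1 − m). Power at m = 5% and 10% is about 0.59 and 0.56 (CRR 30%, ORR 30%), and 0.56 and 0.48 (CRR 10%, ORR 60%).

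**The case against.** The strongest reply is that 12.5 never mentions a denominator. It may only say who can be assigned a response category, and an analyst who follows the cross-references arrives at 33. That is a fair reading, and it is why the bias is stated as conditional. It does not remove the conflict, because nothing tells the analyst to set 12.5 aside. It is also true that 12.5 names only objective response; applying it to CRR is an extension.

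A second reply is that crossing 30% or 10% decides nothing. This stands: 16/33 already has a lower limit of 32.5% and still misses the 17-OR criterion. The effect is on what is reported.

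A third is that k may be small. At k = 1 the shift at the null is 0.9 points on ORR and 0.3 on CRR, against an interval about 32 points wide at 17/33. The first scheduled scan follows cycle 4 (4 × 14 days = 8 weeks), so some loss before it is plausible. But footnote 10 of Section 7 also calls for evaluation at suspected progression, which keeps scanned early progressors inside 12.5. A reader might infer heavy early loss from the median survival below 6 months in Section 1.3. That figure is for patients who are not candidates for high-dose therapy and transplant, a restriction the eligibility criteria do not impose.

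A reader might also infer that 12.5 lets the trial succeed wrongly or pushes type I error above 0.05. The documents do not support this. It would require replacement, which no section provides for, and more than 8.9% unassessed.

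**Conclusion.** The inconsistency is real and should be fixed. Section 12.5 is a stated rule which, used as the denominator, can only raise the reported ORR and CRR and their score limits. The factor on the rates is 33/(33 − k), or 1.03 to 1.18 for an assumed k of 1 to 5. One dropped subject is enough to move the ORR lower limit past the 30% null when there are 15 responders.

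The conclusion rests on 12.5 being read as the denominator and on subjects outside it having no confirmed response. The size rests on k, which is not documented. It concerns estimates and intervals only: the go/no-go rule and its error rate stand with 33 subjects and no replacement.

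**What to change.** Rewrite 12.5 so that the primary ORR and CRR and their score intervals use all subjects counted in the 17 and the 33, in line with 9.3.2, 9.3.3, 12.3 and 12.6. State that any subject without a post-baseline response assessment counts as a non-responder for both OR and CR. Keep the re-evaluated subset as a labelled sensitivity analysis, with the number excluded and the reasons.

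This takes one paragraph and no new data. The cost is slightly lower reported rates than under 12.5.

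Replacement of unassessed subjects is a separate design choice and is not needed for this correction. If the sponsor states a policy, it should show both costs from step 5 with their assumptions: type I error with replacement, and power without it against the stated 0.62.
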